8.5. Hypersensitivity/Anaphylaxis

The event of anaphylaxis is considered as a PDAESI. The information about all suspected anaphylaxis and hypersensitivity events will be recorded on the Suspected Anaphylaxis CRF. PDAESI will be summaries (Section 8.3).

Suspected anaphylaxis data will be listed.

8.6. Deaths

If any patient dies during the study, all relevant information will be discussed in the patient narrative included in the clinical study report.

8.7. Clinical Laboratory Tests

Clinical laboratory tests (serum chemistry, hematology, coagulation, and urinalysis) will be performed at the time points detailed in Table 2 of the study protocol. Clinical laboratory tests will be performed using the central laboratory.

Laboratory test result that is judged by the investigator as clinically significant will be recorded both on the source documentation and the CRF as an adverse event and monitored as described in Section 7.1.2 of the study protocol. (Note: Abnormal laboratory or diagnostic test results at the screening visit that preclude a patient from entering the study or receiving IMP are not considered adverse events.)

Laboratory test results will be presented in standard international (SI) units in summaries. Laboratory values and changes from baseline to each visit and Last Assessment will be summarized using descriptive statistics. Shifts (below [low], within [normal], and above [high] the normal range) from baseline to each postbaseline visit and the Last Assessment will be summarized using patient counts. Baseline is defined as the last observed data before the administration of the first dose of the IMP (also see [Section 4.2](#)).

The potentially clinically significant abnormal values will be derived using criteria specified in [Table 3](#) based on all postbaseline values (including scheduled, unscheduled, and withdrawal visits). The overall incidence of potentially clinically significant abnormal values will be summarized for laboratory variables using descriptive statistics by treatment group. Listings for patients who have potentially clinically significant abnormal laboratory data will be presented.

Note that: The ULN for some test parameters may depend on demographic parameters such as gender (e.g. creatine phosphokinase).

Table 3: Criteria for Potentially Clinically Significant Laboratory Values

Test	Criterion value
Serum chemistry	
Alanine aminotransferase (ALT)	$\geq 3x$ ULN
Aspartate aminotransferase (AST)	$\geq 3x$ ULN
Alkaline phosphatase (ALP)	$\geq 3x$ ULN
Gamma-glutamyl transpeptidase (GGT)	$\geq 3x$ ULN
Lactate dehydrogenase (LDH)	$\geq 3x$ ULN
Blood urea nitrogen (BUN)	≥ 10.71 mmol/L
Creatinine	≥ 177 μ mol/L
Bilirubin (total)	≥ 34.2 μ mol/L
Creatine phosphokinase	$\geq 3x$ ULN
Hematology	
Hematocrit Men	<0.37 L/L
Women	<0.32 L/L

Test	Criterion value
Hemoglobin Men	≤ 115 g/L
Women	≤ 95 g/L
WBC counts	$\leq 3 \times 10^9$ /L $\geq 20 \times 10^9$ /L
Absolute neutrophil count (ANC)	$\leq 1 \times 10^9$ /L
Platelet counts	$\leq 75 \times 10^9$ /L $\geq 700 \times 10^9$ /L
Urinalysis	
Hemoglobin	≥ 2 unit increase from baseline
Glucose	≥ 2 unit increase from baseline
Ketones	≥ 2 unit increase from baseline
Total protein	≥ 2 unit increase from baseline

ULN=upper limit of normal range; WBC=white blood cell

8.7.1. Other Clinical Laboratory Tests

At screening, patients will be tested for hepatitis B surface antigen (HBsAg), antibodies to hepatitis C virus (HCV), human immunodeficiency virus (HIV) types 1 or 2, and Tuberculosis test.

At screening, women who have been amenorrheic for at least 1 year without an alternative medical cause will have a serum follicle stimulating hormone (FSH) assessment to confirm postmenopausal status.

Beta human chorionic gonadotropin (β -HCG) tests in urine will be performed for women of childbearing potential as detailed in Table 2 of the study protocol.

Testing of patients asymptomatic for COVID-19 active infection may be conducted at the discretion of the investigator within 72 hours of any visit. COVID-19 testing may be conducted by the central laboratory or locally.

Other clinical laboratory tests results will be listed.

8.8. Physical Examinations

Physical examinations will be performed at the time points detailed in Table 2 of the study protocol.

Any physical examination finding that is judged by the investigator as clinically significant (except at the initial screening visit, which will be captured as medical history) may be considered an adverse event, recorded on the CRF and the source document, and monitored as described in Section 7.1.2 of the study protocol.

Abnormal physical examination findings will be listed and summarized descriptively.

8.9. Vital Signs

Vital signs (pulse rate, blood pressure [systolic/diastolic], respiratory rate, and body temperature) will be measured at the time points detailed in Table 2 of the study protocol. Any vital sign value that is judged by the investigator as clinically significant will be recorded both on the source documentation and the CRF as an adverse event, and monitored as described in Section 7.1.2 of the protocol.

Height and weight will be obtained at the time points detailed in Table 2 of the study protocol.

Vital signs (including weight and BMI) values and changes from baseline to each visit and the Last Assessment will be summarized using descriptive statistics. The incidence of potentially clinically significant abnormal values will be summarized for selected vital signs using descriptive statistics. Baseline is defined as the last observed data before the administration of the first dose of the IMP (also see Section 4.2).

Table 4 specifies the criteria for identifying vital signs as potentially clinically significant abnormal values. Note that in order to qualify as potentially clinically significant abnormal, a value needs to meet both criteria below: ie, have a value beyond the criterion value and a change of at least the magnitude specified in the change relative to baseline column. The potentially clinically significant abnormal vital signs values will include all postbaseline values (including scheduled, unscheduled, and early withdrawal visits) for the summaries.

Table 4: Criteria for Potentially Clinically Significant Vital Signs

Vital Sign	Criterion value	Change relative to baseline
Pulse	≥120 bpm	Increase of ≥15 bpm
	≤50 bpm	Decrease of ≥15 bpm
Systolic blood pressure	≥180 mm Hg	Increase of ≥20 mm Hg
	≤90 mm Hg	Decrease of ≥20 mm Hg
Diastolic blood pressure	≥105 mm Hg	Increase of ≥15 mm Hg
	≤50 mm Hg	Decrease of ≥15 mm Hg
Temperature	≥38.3°C	Change of ≥1.1°C
Respiratory rate	>24 breaths/min	Increase ≥=10
	<6 breaths/min	Not applicable

Bpm=beats per minute

8.10. Electrocardiography

A 12-lead ECG will be recorded at the time points detailed in Table 2 of the study protocol. ECGs should be performed in a supine position. Standard ECG parameters will be recorded using a centralized process and the ECG will be interpreted locally by the principal investigator (or qualified physician). Additionally, a qualified central reader will interpret all ECG. In cases of disagreement, the interpretation by the central reader should be used. All ECG results outside

the reference ranges will be judged by the investigator (or qualified physician) as belonging to one of the following categories:

- abnormal and not clinically significant
- abnormal and clinically significant

Any ECG finding that is judged by the investigator (or qualified physician) as clinically significant (except at the screening visit) will be considered an adverse event, recorded on the source documentation and in the CRF, and monitored as described in Section 7.1.2 of the study protocol.

Where triplicate measurements are required (at DoR), each ECG will be taken within 1 to 5 minutes of the previous one.

At DoR visit ECG will be performed in triplicate, each ECG will be taken within 1 to 5 minutes of the previous one. For analysis purpose, the mean of recorded results from the 3 measurements will be calculated and used for the analysis. For ECG findings, the last measurement before the first dose of IMP will be used for analysis.

ECG variable results and changes from baseline to each visit and the Last Assessment will be summarized using descriptive statistics.

Baseline ECG findings and shifts (normal, abnormal not clinically significant, and abnormal clinically significant) from baseline to each visit, overall (worst value for a patient), and the Last Assessment will be summarized using patient counts.

In addition, the incidence of patients meeting the following potentially clinically significant thresholds will be presented using descriptive statistics:

- Combined absolute QTc Bazett and Fridericia interval prolongations plus change from baseline in QTc Bazett and Fridericia interval to week 52 and endpoint
 - QTc interval >450 msec and QTc interval increases from baseline >30 msec
 - QTc interval >450 msec and QTc interval increases from baseline >60 msec
 - QTc interval >500 msec and QTc interval increases from baseline >30 msec
 - QTc interval >500 msec and QTc interval increases from baseline >60 msec
- QRS duration >110 msec and a 25% increase from baseline
- PR interval >200 msec and a 25% increase from baseline

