During the treatment period (baseline/day of randomization [DoR, V3] through week 16 [V9]), patients will perform morning lung function assessments (FEV₁ and PEF) by handheld device prior to morning asthma maintenance medication and prior to rescue medication use (whenever possible), assess and record daytime and night-time asthma symptom scores, record rescue medication use (number of puffs) twice daily and confirm (in the evening) that they have taken that day's asthma maintenance medication. During the treatment period visits, formal pulmonary function testing (as required) will be completed in the morning between 0530 and 1100±1 hour on the study-provided spirometry equipment. If a patient has taken rescue medication within 6 hours of the planned pulmonary function testing or has taken the morning dose of asthma maintenance medication, the testing should be cancelled, and the visit should be rescheduled. All formal pulmonary function testing should be conducted at approximately the same time of day ±1 hour of the time it was conducted at baseline/DoR (V3). Other procedures for each visit are outlined in [Table 2](#).

Patients who complete week 16 (end of treatment visit [EoTV; V9]) will enter the follow-up period. The handheld device and diary, along with study provided rescue medication will be collected. The investigator should determine and implement appropriate asthma therapy (including rescue treatment) to be used during the follow-up period. Medication started for the purpose of ongoing asthma treatment will not be considered a protocol violation, provided it is started after the final spirometry assessments are completed at week 16 (V9). Patients will be contacted approximately monthly by telephone to assess CAEs, adverse events, and concomitant medications. A final follow-up visit will occur at approximately week 30 for final assessments. A CAE is defined as worsening asthma requiring treatment with a systemic corticosteroid for ≥3 days, emergency room visit resulting in systemic corticosteroid treatment or hospitalization due to asthma. All instances of a CAE should be recorded in the CRF.

Alert criteria for individual patients who develop worsening asthma have been designed to ensure patient safety. If any of the criteria listed below are met, the investigator will determine whether the patient's overall clinical picture is consistent with worsening asthma and if the

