2. STUDY DESIGN

2.1. General Design

This is a multicenter, randomized, double-blind, placebo-controlled, parallel-group study to evaluate the safety and efficacy of TEV-53275 administered subcutaneously (sc) at doses of 600 mg and 1200 mg or placebo in adult patients with moderate to severe asthma with an eosinophilic phenotype.

Patients may be eligible to participate if they have a diagnosis of asthma for at least 6 months and their current asthma maintenance therapy has been stable for at least 1 month and includes 1 of the following (see Appendix F in the study protocol):

- medium or high dose inhaled corticosteroid (ICS)±another controller
- any fixed dose combination ICS (low, medium or high) with a long-acting β -adrenergic agonist (LABA)±another controller

The patient will continue on this asthma maintenance therapy throughout the treatment period [V9/end of treatment visit (EoTV)]. For patients taking once-daily inhaled treatment, it must be taken in the morning to enable trough lung function assessments. If a patient requires a change in the timing of dosing, it is allowable as long as the investigator believes there is no inherent harm in changing the timing of the dose and the patient agrees to such change.

The study will consist of 4 periods:

- screening period of up to approximately 2 weeks
- run-in period of approximately 14 days
- double-blind treatment period of 16 weeks
- follow-up period of approximately 14 weeks beginning at the end of the double-blind treatment period

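### The QTc outlier summary names a week 52 that this study does not have, and its joint thresholds leave some patients with QTc above 500 msec, or a rise above 60 msec, out of the count

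*SAP*

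**What the plan says.** SAP 8.10 plans three kinds of ECG output: descriptive statistics of values and changes, shift tables of the normal/abnormal reading, and a count of patients who pass set thresholds. For QTc, the third output combines an absolute prolongation with a change, "plus change from baseline in QTc Bazett and Fridericia interval to week 52 and endpoint". It has four rows. The first is "QTc interval >450 msec and QTc interval increases from baseline >30 msec". The other three have the same form and pair an absolute limit with a rise as follows: 450 with 60, 500 with 30, and 500 with 60 msec.

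No row uses the absolute value alone or the rise alone.

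On the calendar, SAP 2.1 gives a "double-blind treatment period of 16 weeks" and then a "follow-up period of approximately 14 weeks beginning at the end of the double-blind treatment period". Protocol 3.1 says: "A final follow-up visit will occur at approximately week 30 for final assessments". Protocol Table 2 and Appendix B schedule the ECG at V3 (in triplicate), at V9 (week 16) and at the early withdrawal visit. The V10 list has no ECG.

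**The concern.** Change from baseline in ECG findings is a named secondary safety endpoint (Protocol 2.1, SAP 1.1). The threshold count is the only planned output that gives QTc outliers as an incidence by arm, and two features of it need attention.

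First, one of its two time points is not in the visit schedule, and the other carries a label that the SAP defines for a different purpose. A programmer would have to guess what to produce.

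Second, a patient can cross one of the SAP's own limits, 500 msec in absolute value or 60 msec in rise, without meeting the paired condition, and is then in no row. A row could show zero in an arm that contains such a patient.

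**Working it through.** The plan states no figure to reproduce. The check compares the time labels with the visit schedule and then applies the counting rule as written.

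**Step 1: the calendar.** Inputs are V9 at day 112±2 and V10 at day 210±5 (Protocol Table 2).

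- Week 52 = 52 × 7 = day 364.
- Latest V10 = 210 + 5 = day 215, and 215 / 7 = 30.7 weeks.
- Week 52 is 52 − 16 = 36 weeks after the last scheduled ECG and 52 − 30 = 22 weeks after the last visit.
- Total participation is 2 + 2 + 16 + 14 = 34 weeks, so counting from screening does not reach week 52 either.

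**Step 2: the other label.** SAP 6.1 defines endpoint for the efficacy analysis, as the last assessment within 16 weeks. The safety term is Last Assessment (SAP 4.4): the last post-baseline value in the treatment period, with early-withdrawal data included. The rest of 8.10 uses Last Assessment. Each patient has one scheduled post-dose ECG, at V9 or at early withdrawal, so reading endpoint in this way captures nearly all scheduled post-dose ECGs. An unscheduled ECG taken before the last one would not be captured. SAP 4.1 brings all post-baseline values into the outlier summaries for laboratory tests and vital signs but does not mention ECGs.

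**Step 3: the counting rule.** Let b be baseline QTc and v a post-dose QTc. Each row requires v > a and v − b > c, with (a, c) = (450, 30), (450, 60), (500, 30), (500, 60). Every a is at least 450 and every c at least 30, so all four rows lie inside the first. A patient who fails the first row is in none.

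Two groups are left out:

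- **QTc above 500, rise of 30 or less.** Then b ≥ v − 30 > 500 − 30 = 470. In whole msec the smallest such baseline is 471.
- **Rise above 60, QTc of 450 or less.** Then b < 450 − 60 = 390.

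| Baseline (msec) | Post-dose (msec) | Rise (msec) | Rows met |
|---|---|---|---|
| 480 | 505 | 25 | none |
| 505 | 520 | 15 | none |
| 510 | 510 | 0 | none |
| 375 | 445 | 70 | none |
| 380 | 445 | 65 | none |
| 470 | 501 | 31 | >450 and >30; >500 and >30 |
| 440 | 505 | 65 | all four |

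The range of post-dose values above 500 that go uncounted widens with baseline: 501 only at baseline 471, 501 to 510 at 480, 501 to 520 at 490, and 501 to 530 at 500.

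**Step 4: size.** With 300 patients randomized 1:1:1, each arm has about 100, so one uncounted patient is 1/100, or about 1 percentage point in that arm. The eligibility and randomization criteria (Protocol 4.1 to 4.3) set no QTc limit, so a baseline above 470 msec is not excluded by a QTc criterion. The documents give no QTc distribution, so no expected number can be calculated.

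**Step 5: with stand-alone rows.** 480 to 505 and 505 to 520 enter the >450 and >500 rows. 375 to 445 enters the rise >30 and rise >60 rows.

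**The case against.** A reader might infer that the summary cannot produce data. The documents do not support that. The line names two time points, and the endpoint half can be filled from V9 or the early withdrawal visit. There is no table shell in the documents, so an empty week 52 column is itself an inference. What stands is a wrong label beside a usable but misassigned one.

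A reader might also infer that a QTc above 500 msec could go unnoticed. That is not supported either. SAP 8.1 lists all safety data. The descriptive statistics include the maximum (SAP 4.1). The shift table uses the worst reading per patient. Every ECG is read centrally, and any finding judged clinically significant becomes an adverse event. What these outputs lack is a by-arm count against a QTc threshold.

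The joint rule is also not a drafting slip. The SAP labels the rows as combined, applies the same convention to most vital signs (Table 4 in SAP 8.9), and pairs an absolute value with a 25% increase for QRS and PR. No passage promises a stand-alone count, so nothing is contradicted. The convention is not universal, however. A respiratory rate below 6 counts without any change condition, and the chemistry and hematology limits in SAP Table 3 use values alone.

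Finally, the Protocol gives no particular cardiac signal: cardiac events are not among its events of special interest, and its Phase 1 safety summary names none. That supports a low priority.

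**Conclusion.** The point holds on both parts, in limited form, and is minor.

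- **Time point.** Week 52 is an error in an operative analysis rule, and endpoint needs to be brought into line with the safety definition. If endpoint is read as the last value on treatment, little scheduled ECG data is lost.
- **Joint thresholds.** This is a deliberate choice with a gap, not a contradiction. The outlier table does not count QTc above 500 msec with a rise of 30 msec or less, or a rise above 60 msec with QTc of 450 msec or less. These patients remain visible individually and possibly in the shift table or as adverse events, but no planned output counts them by arm.

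The number affected is probably small, because the first group needs a baseline above 470 msec. That is a judgment, since no QTc distribution is given. The 1 percentage point per patient assumes about 100 per arm.

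**What to change.** In SAP 8.10:

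1. Replace the week 52 and endpoint wording with week 16 (V9), Last Assessment, and any post-baseline ECG including early withdrawal and unscheduled ones. The last item matches what SAP 4.1 already does for laboratory tests and vital signs.
2. Keep the four combined rows and add stand-alone rows for QTc >450, QTc >500, rise >30 and rise >60 msec. All four thresholds are already in the SAP.
3. Present Bazett and Fridericia separately.

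The cost is SAP wording and a few table rows. No new ECGs or other data are needed.

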8.11. Concomitant Medications or Therapies

Concomitant medications, treatments, or procedures will be collected up to the end of study.

All concomitant medications will be coded using the WHO Drug. The incidence of concomitant medications will be summarized using descriptive statistics by therapeutic class and preferred term. Patients are counted only once in each therapeutic class category, and only once in each

preferred term category. The concomitant medications will include all medications taken after administration of the first IMP.

Asthma medications will be summarized by the medication class separately.

9. TOLERABILITY VARIABLES AND ANALYSIS

Number (%) of patients who did not complete the study due to adverse events will be summarized descriptively.

[REDACTED]

[REDACTED]

[REDACTED]

[REDACTED]

[REDACTED]

[REDACTED]

[REDACTED]

[REDACTED]

[REDACTED]

12. IMMUNOGENICITY ANALYSIS

Immunogenicity analyses are outside of the scope of this SAP.

Listing(s) of patients with positive ADA sample(s) and patient ADA status will be provided if applicable.

13. PLANNED INTERIM ANALYSIS

The final primary efficacy analyses will be performed when all patients have completed V9 (week 16) or withdrawn from study.

An unblinded interim analysis is planned, when approximately 120 patients (40 patients per arm) have completed the week 8 visit or withdrawn from the study, to assess the early efficacy data. The objectives of the unblinded interim efficacy analysis are: 1) to detect an early efficacy success signal; 2) to conduct a formal futility analysis, so that the study may be terminated early if both TEV-53275 dose groups are futile, ie, meet the futility criterion; and 3) to evaluate early stopping criteria. These analyses will be described in details in Section 13.1.

At the time of the interim analysis, a blinded safety analysis will be conducted. If there is any safety signal of concern at the time of the interim analysis, unblinded safety analyses may be warranted.

[REDACTED]

13.1. The Unblinded Interim Efficacy Analysis

For the early efficacy success and futility analysis, the week 8 efficacy endpoint, ie, change from baseline at week 8 in morning trough FEV₁, will be analyzed. However, the feasibility of stopping the trial earlier with a smaller sample size is evaluated based on the week 12 efficacy endpoint, ie, change from baseline at week 12 in morning trough FEV₁.

The same Bayesian analysis for the final primary efficacy analysis will be applied to the week 8 and week 12 endpoints, as applicable, to derive the posterior probability of the TEV-53275 dose group performing better than the placebo group in terms of the week 8 endpoint and the posterior probability of the TEV-53275 dose group performing better than the placebo group in terms of the week 12 endpoint using the interim analysis data.

13.1.1. [REDACTED]

[REDACTED]

13.1.2.

13.1.3. Early Stopping with a Smaller Sample Size

Due to challenges in patient enrollment in the face of COVID-19 pandemic, the feasibility of an early stopping of the trial with smaller sample sizes will also be evaluated during the interim analysis. The unblinded assessment is based on

Posterior probability (TEV-53275 1200 mg treatment effect vs placebo >0 at interim analysis) for the primary efficacy endpoint (12-week endpoint).

The final trial sample size would be reduced to a smaller number according to the following criteria:

1. Reduce to 80 per arm in case of “Very good” efficacy signal:

Posterior probability ≥ 0.95 ;

2. Reduce to 90 per arm in case of “Good” efficacy signal:

$0.95 > \text{Posterior probability} \geq 0.9$;

3. Keep 100 per arm when the efficacy signal is not as good, but not futile:

Posterior probability < 0.9 .

Simulations were conducted to assess the operating characteristics of the early stopping rules. The simulations took into account the non-binding futility stopping specified in Section 13.1.2. When the futility criterion is met, a simulated trial is stopped due to futility with a probability of 50% or 30%. For the purpose of estimating type 1 error rates and study powers using simulations, the posterior distributions for the mean responses were derived using the conjugate priors for the means with a known standard deviation of 0.35 L in the Bayesian analysis. The priors follow normal distributions with mean 0 for all treatment groups. The simulations assumed a 10% dropout rate and 5000 simulations run were used in each scenario.

Table 6 below summarizes the simulation results for a range of treatment effects, including the overall study power under the study design, the probability of meeting the “Very good” and “Good” efficacy criteria at the interim analysis, as well as the conditional power given that the sample size reduction criteria are met at the interim analysis. The results showed that the early stopping rules didn’t compromise the type 1 error control (controlled at 15% under the null hypothesis). The overall study power is maintained at approximately the same level (approximately 80% when the high-dose treatment effect=0.1L). In addition, it is reassuring that, when the early stopping criteria are met and the sample size is reduced, the conditional power is high ($>94\%$ in all scenarios). It ensures that the decision to stop early with a smaller sample size is made with high assurance of final success, despite a smaller sample size to be used. It’s also worth noting that there is a 44% to 68% of chance to meet the early stopping criteria due to “Very good” and “Good” efficacy results under the alternative hypotheses, but an approximately 10% chance under the null hypothesis.

[REDACTED]						
[REDACTED]						
[REDACTED]						
[REDACTED]						
[REDACTED]						
[REDACTED]						
[REDACTED]						
[REDACTED]						

From a practical standpoint, if the site personnel learned about the plan for the early stopping with reduced sample size using the unblinded assessment of interim data, there can be a potential unblinding and biasing risk. When the decision is made to early stop the trial with a smaller sample size, the site personnel can guess about the treatment efficacy and it can bias their views. Therefore, favorable actions may be taken towards the active treatment subconsciously or consciously. In order to alleviate this concern, the early stopping plan is concealed in the protocol amendment 1, but is only described in the SAP. When a decision on early stopping is made, it will be documented and the reduced sample size (240 or 270) will be communicated to the study team. However, in order to minimize the potential risk of biasing the site personnel, the decision will not be revealed to sites until the enrolment is close to reaching the reduced sample size goal.

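### Does the sample-size-reduction rule in SAP 13.1.3 push type 1 error above the stated 15% once the non-binding futility stop is ignored?

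*SAP*

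**What the plan says.** SAP 13.1.3 bases the reduction on the posterior probability that 1200 mg beats placebo. The final size is 80 per arm if that probability is at least 0.95, 90 if it lies between 0.90 and 0.95, and 100 otherwise. SAP 13.1 says that "the feasibility of stopping the trial earlier with a smaller sample size is evaluated based on the week 12 efficacy endpoint". The interim itself is triggered when about 40 patients per arm have completed week 8 or withdrawn (SAP 13). The final success threshold is 0.85 (Protocol 9.13.1), and no adjustment of it for the reduction is described.

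On operating characteristics, SAP 13.1.3 says: "The simulations took into account the non-binding futility stopping specified in Section 13.1.2". It adds: "When the futility criterion is met, a simulated trial is stopped due to futility with a probability of 50% or 30" per cent. It also says "The simulations assumed a 10% dropout rate and 5000 simulations run were used in each scenario", and "The priors follow normal distributions with mean 0 for all treatment groups". The SAP concludes that the rules did not "compromise the type 1 error control (controlled at 15% under the null hypothesis". It reports that "there is a 44% to 68% of chance to meet the early stopping criteria" under the alternatives, "but an approximately 10% chance under the null hypothesis", with conditional power above 94% and overall power of about 80% at 0.1 L.

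The futility criterion (13.1.2) and the cells of Table 6 are blacked out. The variance of the simulation's priors cannot be read.

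**The concern.** There are three reasons to doubt the 15%.

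- **The rule acts in one direction.** The sample is cut only after a good interim, so favourable early data are diluted by fewer later patients. With the final threshold unchanged, false positives must rise somewhat.
- **The simulations took credit for futility stops that the sponsor need not make.** A trial stopped under the null cannot become a false positive. The usual basis for type 1 error under a non-binding rule is that the stop is never used, and the readable text names only 50% and 30% stopping.
- **The simulation is coarse.** With 5000 runs, the error of the estimate is as large as the effect in question.

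If the true rate were well above 15%, the SAP would be misdescribing its primary decision rule and using that description to justify an unblinded adaptation.

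**Working it through.** **Inputs.** SD 0.35 L, effect 0.1 L and one-sided 15% (SAP 2.4); final threshold 0.85 (Protocol 9.13.1); cut-offs 0.90 and 0.95, 10% dropout and zero-mean normal priors (SAP 13.1.3). With 10% dropout, final sizes of 80, 90 and 100 become 72, 81 and 90 evaluable per arm. Two quantities are assumed: the number per arm with week 12 data at the interim, n1 = 20 to 36 (36 = 90% of 40), and the prior SD τ for each arm mean.

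**Reproducing the SAP's fixed-design power.** Protocol 9.1 assumes 15% and 8% dropout, giving 85 and 92 of 100. Then 0.1 / (0.35 × √(1/85 + 1/92)) = 1.899, and Φ(1.899 − 1.036) = 80.6%. This matches SAP 2.4.

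**Model.** Let Z be the standardised difference with n per arm and w = τ²/(τ² + 0.35²/n). The posterior probability of benefit is Φ(√w · Z), so a cut-off p corresponds to Z ≥ z(p)/√w. Under a flat prior w = 1, and the cut-offs are 1.645 (0.95), 1.282 (0.90) and 1.036 (0.85). Given interim value z, the chance of final success under the null with n per arm is

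A(z, n) = 1 − Φ[(c − z√(n1/n)) / √(1 − n1/n)], where c is the final cut-off.

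Type 1 error is the integral of φ(z)·A(z, n) over z, with n = 72 above the upper cut-off, 81 between the two, and 90 below. No futility stop is applied.

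**Size at one point.** Take n1 = 32, a flat prior and z = 1.645. A(z, 90) = 1 − Φ(0.069) = 47.2%, and A(z, 72) = 1 − Φ(−0.081) = 53.2%. The rule therefore adds about 6 points there, but only 10% of null trials reach either reduction region.

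**Full integral, n1 = 32, flat prior.**

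| Interim region | With rule | Always 90 |
|---|---|---|
| Posterior ≥ 0.95 | 3.33% | 2.95% |
| 0.90 to 0.95 | 2.18% | 2.07% |
| < 0.90 | 9.97% | 9.97% |
| Total (unrounded sum) | 15.48% | 15.00% |

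**Across assumptions, futility ignored.**

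| Prior SD | n1 = 20 | n1 = 27 | n1 = 36 | Without rule |
|---|---|---|---|---|
| Flat | 15.32% | 15.41% | 15.53% | 15.00% |
| 0.35 L | 15.17% | 15.26% | 15.38% | 14.87% |
| 0.2 L | 14.86% | 14.95% | 15.07% | 14.60% |

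The increase runs from 14.86 − 14.60 = 0.26 points to 15.53 − 15.00 = 0.53 points. A tight prior (SD 0.1 L, n1 = 36) gives 13.80% against 13.46% without the rule.

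**Fit to the SAP's visible outputs.** At n1 = 32 with a flat prior, the model gives a 10.0% chance of reduction under the null, 44.5% at 0.1 L, conditional power of 94.2% and power of 80.8%. These agree with the SAP's approximately 10%, 44%, above 94% and about 80%, provided the 44% belongs to the 0.1 L effect, which the SAP does not say.

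**Precision of the sponsor's run.** √(0.15 × 0.85/5000) = 0.50 points. If the true rate were 15.5%, 5000 runs would typically return 14.5% to 16.5%.

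**Credit from futility.** SAP 13 requires both doses to be futile. The cut-off is unknown. As an assumption, apply one to the same week 12 data with n1 = 32 and a flat prior. At a posterior cut-off of 0.3 for both doses, stopping 30% or 50% of such trials lowers type 1 error by about 0.1 points. At 0.2 it falls by no more than 0.05 points. A cut-off near 0.5 is needed for 0.4 to 0.6 points.

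**The case for a change.** The strongest case for a change is that the direction of the effect is not in doubt. The rule raises type 1 error under every prior tried. Under the weak prior that best fits the SAP's other visible figures, the total with futility ignored is about 15.5%, not 15.0%. The readable method describes only simulations with futility credit, and 5000 runs could not have revealed the difference. One larger null run with no futility stops would settle it cheaply: 100,000 runs give a standard error of 0.11 points.

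The direction and size stand. The inference that the SAP's claim is unsupported does not:

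- The results table is blacked out, so a row with no futility stopping may already be there.
- The SAP does not say that the rule has no effect. It says that control at 15% is not compromised, and gives a whole number.
- At a prior SD of 0.2 L, the total with futility fully ignored is 14.9% to 15.1%, so the statement holds as written. The weak-prior reading depends on assigning the 44% to 0.1 L.
- Depending on the hidden criterion, futility credit may be almost nothing, so removing it might leave the reported figure unchanged.

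**Conclusion.** No change is needed. With the futility stop ignored and the threshold kept at 0.85, the reduction rule adds about 0.3 to 0.5 points, for a total of about 14.9% to 15.5%. This assumes a known SD of 0.35 L, 10% dropout, 20 to 36 per arm with week 12 data at the interim, and a zero-mean prior with SD of 0.2 L or wider. The stated 15% is not shown to be wrong: most of the range rounds to it, and the sponsor's simulation could not separate the two ends.

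The criterion is a Phase 2 go/no-go rule at one-sided 15%, with no multiplicity adjustment (SAP 7). Half a point does not alter how a success or failure would be read, and the plan followed as written gives a sound decision at about the advertised error rate. Resetting the threshold would aim at precision that the unknown prior and interim numbers do not support. If Table 6 lacks a row with no futility stopping, adding one and describing the rate as approximate would be a courtesy to readers. It would not correct an error.
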